### **Validity and reliability**

Women with GDM in the intervention and control group were divided into groups by randomization method. Women with GDM who were followed up in the perinatology clinic were divided into groups by means of a lottery method. In the clinic, women in

the same room were not taken to different groups to avoid problems among GDM women.

In this study reliability of the instruments was measured with Cronbach's alpha. The Cronbach's alpha value of the HPLP II was 0.90; the CES-D was 0.85 and the SF-36 was 0.85.

### **Ethical considerations**

The required permissions were obtained from the Clinic Research Ethics Committee of Zeynep Kamil Women and Children Diseases Education and Research Hospital. All participants gave informed consent prior to inclusion in the study. Participants were informed that they could leave the study if they wanted. All contact numbers were given to the participants for any inquiries.

### **Data analysis**

The data were analysed using the SPSS 21 package. The introductory information derived from the introductory form administered to the participants in the intervention and the control group were analysed using descriptive statistical methods and compared using the Chi-square ( $\chi^2$ ) test and Mann-Whitney test. Pre-post test results of women in the intervention group were compared using the Wilcoxon Signed Rank Test. The first, second and third assessments of the intervention group were compared using the Wilcoxon Signed Rank Test, while the first and third (postpartum 6th month) assessments of the intervention and the control groups were compared using the Mann-Whitney test. Postpartum characteristics of the neonates were analysed using the Chi-square ( $\chi^2$ ) test and Mann-Whitney test. Lastly, the postpartum diabetes controls of the intervention and control groups were compared using Fisher's exact chi-square test.

[figure not shown]

Figure 1. Flowchart of this study

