## **Desing**

The study was designed and conducted as a two group quasi-experimental study. Intervention group (n=46) and control group (n=42) were administered the data collecting tools in the first assessment. After first assessment, the intervention group were included in the educational program. Data collecting tools were re-administered four weeks after to the intervention group only. Than data collecting tools were re-administered to the both groups in the postpartum 6th week.

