## **Sample**

This study was conducted in the perinatology clinic of the Istanbul Zeynep Kamil Hospital, Turkey in 2015. The records show that 350 women with GDM were referred to the perinatology clinic in that period. The sample size was calculated using Power and Sample Size Program, with 80% power and a 0.05 margin of error, and it was

determined that both the intervention and the control group should include at least 30 women with GDM. It was considered appropriate that 50 women with GDM be included in each group.

The inclusion criteria for participation in the study included a gestational period of 24 to 34 weeks, a diagnosis of GDM, an age of 18 years or older, and voluntary consent to participate in the study, while the exclusion criteria included the presence of a psychiatric disease, multiple pregnancy, the risk of preterm labor, placenta previa or premature rupture of the membranes, and failure to obtain voluntary consent to participate in the study.

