#### *Secondary outcomes*

- Postpartum diabetes control of women with GDM was assessed through the postpartum 6th week information form that developed by the researchers on the basis of the literature.
- Postpartum characteristics of neonates were assessed through the neonate's information form that developed by the researchers on the basis of the literature.

The flowchart of this study is shown in Figure 1. The patients followed up in the perinatology clinic were assigned to groups through randomization (drawing lots by the clinic nurse). Data collector checked patients in the perinatology clinic daily. If there were more than one patient who met the inclusion criteria, it was determined which group to take with the lottery method. When there was only one woman with GDM in the clinic, it was determined which group to take with the lot but the next patient was taken directly to the opposite group. When two patients were in the same room, they were taken into the same group in order not to have any ethical problems. The women in the both group were administered the introductory information form, the HPLP-II, the CES-D and the SF-36 in the first assessment.

The education program and also usual care applied to the intervention group. The education program consisted of three 45-min sessions, which included a face-to-face lecture with the dissemination and presentation of written and visual materials. Also each participant in the intervention group was given the *Health-Promoting Lifestyle Booklet* and the *Diary of a Woman with GDM* card. The booklet features all of the health-promoting practices (self-monitoring of blood glucose, nutrition, physical activity, stress, sleeping, smoking, self-care and breastfeeding). The *Diary of a Woman with GDM* card features the daily program that women should follow (the hours for main meals and snacks, insulin hours, etc.). The education and counseling were maintained through follow-up via phone for intervention group.

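### Neonatal outcomes and postpartum diabetes control are compared without any covariate, although allocation was not fully random and baseline tests at 46 v 42 leave imbalances of up to about 0.42 SD unflagged

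*Combined protocol and SAP*

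**What the plan says.** **Introductory characteristics.** According to the Data analysis section, details from the introductory form "in the intervention and the control group were analysed using descriptive statistical methods and compared using the Chi-square" and Mann-Whitney tests. The plan thus has descriptive summaries and significance tests. It gives no standardised differences, no list of prognostic covariates and no rule for acting on an imbalance.

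**Outcomes at issue.** The same section states: "Postpartum characteristics of the neonates were analysed using the Chi-square" and Mann-Whitney tests. Postpartum diabetes control is compared by Fisher's exact test. No regression, stratified or otherwise adjusted analysis appears anywhere in the document.

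**Design and allocation.** The Desing section calls the study "designed and conducted as a two group quasi-experimental study". The allocation text under Secondary outcomes describes drawing lots, with two departures. After a lone eligible woman has been drawn by lot, the next woman goes to the other group without a draw. Women sharing a room are kept in one group, a rule that Validity and reliability repeats.

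**Numbers.** "Intervention group (n=46) and control group (n=42) were administered the data collecting tools in the first assessment".

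**The concern.** HPLP-II, CES-D and SF-36 have first-assessment scores. Neonatal outcomes and postpartum diabetes control cannot have them, so entry characteristics are the natural source of adjustment for H4 and for diabetes control. The plan compares those characteristics between groups but does not carry them into either outcome analysis.

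This matters more here than in a fully randomised trial. A forced assignment can be foreseen, and room-mates are not allocated independently, so a difference between the groups at entry need not be due to chance alone. A p-value is also a poor guide to whether such a difference matters. What counts is its size and how strongly the characteristic predicts the outcome. A moderate, prognostic imbalance could go unflagged and feed directly into the neonatal comparison.

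**Working it through.** **The plan's own calculation.** The Sample section reports a calculation "with 80% power and a 0.05 margin of error", giving at least 30 women per group. It states no effect size, SD, event rates, endpoint or test, so the figure cannot be reproduced. Back-solving for two means, two-sided, gives √(2/30) × (1.960 + 0.842) = 0.72 SD. That value is not in the documents and says nothing about baseline balance.

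**Inputs from the documents.** n = 46 and 42 at first assessment (Desing). **Assumed:** two-sided 0.05 for the baseline tests, and the imbalances and correlations shown below, because the documents contain no baseline data.

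**Step 1. Largest observed imbalance that stays non-significant.**
- Standard error of a standardised difference: √(1/46 + 1/42) = 0.2134.
- Continuous: t(0.975, 86 df) × 0.2134 = 1.988 × 0.2134 = 0.424 SD.
- Binary: 1.96 × √(p(1−p)) × 0.2134 = 0.167, 0.192 and 0.209 for overall proportions of 20%, 30% and 50%, that is 17 to 21 percentage points.

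**Step 2. Chance of flagging a systematic imbalance of size d.** This applies only if allocation itself created a real difference. Normal approximation with Mann-Whitney efficiency 3/π: power = Φ(d × √(3/π)/0.2134 − 1.96).
- d = 0.3: 28%, so missed about 72% of the time.
- d = 0.4: 45%, so missed about 55% of the time.
- The normal-theory test reaches 80% power only at (1.960 + 0.842) × 0.2134 = 0.60 SD.

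**Step 3. Consequence for an unadjusted outcome test.** Take a covariate with observed imbalance d and correlation ρ with the outcome, no treatment effect, and all 88 women analysed. The group difference is shifted by ρd SD. With m = ρd/0.2134 and s = √(1−ρ²), the conditional type I error of a normal-theory test is [1 − Φ((1.96−m)/s)] + Φ((−1.96−m)/s).

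| d (SD) | ρ = 0.3 | ρ = 0.5 | ρ = 0.7 |
|---|---|---|---|
| 0.2 | 4.9% | 4.5% | 3.4% |
| 0.3 | 6.0% | 7.4% | 8.6% |
| 0.4 | 7.6% | 11.9% | 18.2% |

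At d = 0.4 the shift is 0.12, 0.20 and 0.28 SD respectively. At d = 0.2 there is no inflation.

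**Step 4. The same on the risk scale, all inputs assumed.** The shift in the risk difference is the imbalance in a binary covariate multiplied by the difference in complication risk between its two levels: 0.10 × 0.20 = 2.0 points; 0.19 × 0.20 = 3.8 points; 0.19 × 0.30 = 5.7 points. The shift could favour either group.

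**The case against.** The strongest reply has four parts.

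- **Descriptive summaries are planned.** A reader might infer that comparability is judged by significance tests alone. The text does not support this: group summaries accompany the tests, and a reader can see the size of a difference in them. This stands. It does not repair outcome tests that use no covariate.
- **Lots give some protection.** A reader might infer that entry characteristics are the only safeguard for these outcomes. They are not, because lots were drawn for part of the allocation. Under purely random allocation the unadjusted test keeps its 5% level on average, and an imbalance beyond 0.4 SD arises by chance in only about 6% of cases per covariate (2 × [1 − Φ(0.4/0.2134)] = 0.061). This limits the concern but does not remove it, since allocation departed from pure lots.
- **The plan does not equate non-significance with comparability.** It sets no such rule and draws no such conclusion. The most that can be said is that an imbalance can pass unnoticed if judged by its p-value.
- **No particular confounder is documented.** The diary card provides for "the hours for main meals and snacks, insulin hours, etc", and a reader might infer an uncontrolled imbalance in insulin treatment at entry. The card is a template. It does not show how many women used insulin, when they started, or whether the introductory form recorded it. The form's items are not listed, so a count of false alarms across many baseline tests would also have no source.

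It can also be said that these outcomes are secondary and that the week-6 scale comparisons are equally unadjusted. Both are true, but H4 is a stated hypothesis and rests on the neonatal comparison.

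**Conclusion.** The concern holds in a limited form. Neonatal outcomes and postpartum diabetes control are analysed with no covariate, in a study whose allocation was not fully random and whose baseline tests leave observed imbalances of up to about 0.42 SD, or 17 to 21 points, non-significant. Those limits follow from the document's own group sizes.

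The consequence is conditional. With an assumed 0.4 SD imbalance and a correlation of 0.3 to 0.7 with the outcome, type I error rises from 5% to about 8% to 18%. With 0.2 SD it does not rise. The documents contain no baseline data, so they do not show that the groups differed or that the neonatal result is biased. Adjustment is a cheap improvement to the analysis and not the correction of a demonstrated error.

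**What to change.** 1. Choose one or two prognostic entry characteristics on clinical grounds, without reference to observed imbalance or outcome results. Gestational week at entry is one candidate, since eligibility (24 to 34 weeks) requires it to be known. Treatment at entry is another, if the form or clinic record holds it.
2. Adjust H4 and postpartum diabetes control for them. For binary outcomes use a Mantel-Haenszel risk difference, with any bands of a continuous covariate fixed in the same way. Use Firth logistic regression only if strata are too sparse, and say then that the estimate is an odds ratio. For continuous neonatal outcomes use linear regression.
3. Keep the present unadjusted tests as sensitivity analyses.
4. If outcome data have already been compared, as the past-tense text suggests, label the adjusted analysis post hoc.
5. Replace baseline p-values by standardised differences beside the existing summaries. This improves reporting but by itself changes no result.

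**Cost.** Revised wording and a modest reanalysis, with no new participants. Few events are likely to limit the model to one or two covariates. Adjustment does not remove bias from unmeasured factors or from room clustering.

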The women in the control group which receiving only usual care were followed according to the institution's routine diabetes follow-up protocol (monitoring blood glucose levels as frequently as indicated by the doctor, and patients are referred to dietitian and to diabetes nurse). To assess the effectiveness of the educational program, the HPLP-II, CES-D and SF-36 were re-administered to the intervention group four weeks after the first assessment (second assessment). The HPLP-II, CES-D and SF-36 were re-administered to the both groups in the postpartum 6th week (third assessment).

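### The postpartum week 6 comparison, the only controlled test of H1 to H3, is not adjusted for the first-assessment HPLP-II, CES-D and SF-36 scores collected in both groups

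*Combined protocol and SAP*

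**What the plan says.** Both groups complete the three scales at the start: "The women in the both group were administered the introductory information form, the HPLP-II, the CES-D and the SF-36 in the first assessment" (under Secondary outcomes). The second assessment is one-sided: "the HPLP-II, CES-D and SF-36 were re-administered to the intervention group four weeks after the first assessment (second assessment". The third covers both groups: "The HPLP-II, CES-D and SF-36 were re-administered to the both groups in the postpartum 6th week (third assessment".

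Data analysis names two procedures for these scores. Between groups: "while the first and third (postpartum 6th month) assessments of the intervention and the control groups were compared using the Mann-Whitney test". Within the intervention group: "The first, second and third assessments of the intervention group were compared using the Wilcoxon Signed Rank Test". It names no ANCOVA, rank ANCOVA, mixed model or change-score comparison, and no between-group effect estimate or interval.

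On design, the section headed Desing states: "The study was designed and conducted as a two group quasi-experimental study". On allocation, for a woman who is alone in the clinic, "it was determined which group to take with the lot but the next patient was taken directly to the opposite group". Roommates are placed together in one group.

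**The concern.** The second assessment has no control group and the Wilcoxon tests are uncontrolled. Three of the four hypotheses (lifestyle, depressive symptoms, quality of life) therefore rest on the postpartum between-group comparison. A Mann-Whitney test takes no covariate. Comparing the groups at the first assessment as well does not adjust the later comparison.

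Two things are at stake. The first is precision: a baseline measure of the same scale usually explains part of the follow-up variance, and that gain is forgone. The second is interpretation: a baseline difference carries into the postpartum contrast and can be read as a programme effect. Balance is less assured here than under concealed individual randomisation, because part of the allocation is deterministic and part goes by room.

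**Working it through.** **Inputs from the documents.** 46 and 42 women at the first assessment (Desing). A minimum of 30 per group at 80% power and 0.05 (Sample). Cronbach's alpha 0.85 to 0.90 (Validity and reliability). The text gives no week 6 counts, so 30/30 serves as a low case.

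**Assumptions.** Correlation r between first-assessment and week 6 score of 0.3, 0.5 or 0.7; effect size; score shape.

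**1. The plan's own figure.** The 30 per group cannot be reproduced, because effect size, SD, endpoint and sidedness are not given. Working back with the normal approximation, d = (1.960 + 0.842) × √(2/30) = 0.72 two-sided, or (1.645 + 0.842) × √(2/30) = 0.64 one-sided. The t-test versions are 0.74 and 0.65.

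**2. Normal-theory check.** SE of a mean difference = √(1/46 + 1/42) = 0.213 SD. Adjustment multiplies the SD by √(1 − r²). The difference detectable with 80% power is 2.802 × 0.213 × √(1 − r²): 0.60 SD unadjusted, and 0.57, 0.52 and 0.43 SD at r = 0.3, 0.5 and 0.7. Power at 0.5 SD is 65% unadjusted, and 69%, 77% and 91% adjusted.

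**3. Rank tests, by simulation.** There were 20,000 runs for normal scores and 10,000 for skewed scores (gamma shape 2, Gaussian copula, r on the latent scale). Rank ANCOVA regresses the pooled rank of follow-up on group and the pooled rank of baseline.

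| Case | Mann-Whitney | Rank ANCOVA, r = 0.3 / 0.5 / 0.7 |
|---|---|---|
| 46/42, 0.5 SD, normal | 61-62% | 65 / 73 / 87% |
| 46/42, 0.5 SD, skewed | about 78% | 81 / 87 / 96% |
| 30/30, 0.5 SD, normal | 46% | 49 / 56 / 71% |
| 30/30, 0.5 SD, skewed | 62% | 65 / 72 / 85% |
| 46/42, 0.65 SD, normal | 83% | 86 / 92 / 98% |
| 46/42, 0.74 SD, normal | 91% | 93 / 97 / 99.5% |
| 46/42, no effect | 4.8-5.1% | 4.9-5.3% |

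These runs treat patients as independent.

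**4. Interval width.** The 95% half-width with HC3 errors, normal scores, 46/42, is 0.42 SD unadjusted and 0.41, 0.375 and 0.31 SD adjusted (2%, 11% and 27% narrower).

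**5. Chance imbalance.** P(|baseline difference| ≥ 0.4 SD) = 2 × [1 − Φ(0.4/0.213)] = 6%. Given a realised 0.4 SD imbalance and no true effect, Mann-Whitney rejects in 8%, 12% and 17% of trials, and rank ANCOVA in 5%. At 0.2 SD Mann-Whitney stays at or below 5%. Testing baseline is a weak safeguard: a true 0.3 SD difference would reach significance only about 29% of the time.

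**6. Systematic difference.** For score-scale ANCOVA with baseline reliability *rel*, unadjusted bias = 0.4 × r / *rel* and adjusted bias = 0.4 × r × (1 − *rel*) / *rel*. At r = 0.5:
- *rel* = 0.6: 0.33 SD falls to 0.13 SD.
- *rel* = 0.9: 0.22 SD falls to 0.02 SD.

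Cronbach's alpha measures internal consistency only, so it does not settle *rel*.

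**The case against.** The strongest reply is that this is an efficiency choice and not an invalid test. The correlation between a score in pregnancy and one after birth is unknown, so the small-gain case cannot be excluded. At 0.74 SD, the two-sided effect implied by 30 per group, Mann-Whitney already has 91% power and gains only 2 to 8 points. The raised error rates condition on an imbalance that chance produces in 6% of trials. All of this stands, and it limits how serious the point is. It does not justify leaving a collected baseline score out of the key comparison.

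A second reply is that the study is already conducted, so replacing the main test opens room for analytic choice. In normal-score simulations at 0.5 SD the two tests give different verdicts in 9%, 16% and 29% of trials (r = 0.3, 0.5, 0.7). This is a real cost. It is why the change must be labelled post hoc and the Mann-Whitney result shown beside it.

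Third, several figures have limits:
- The bias reductions in step 6 are for score-scale ANCOVA, not for the rank test.
- If all patients came in same-group pairs with an assumed ICC of 0.1 to 0.2, type I error would be about 5-8% for both tests.
- With an assumed five-level score and half the women at the ceiling, the gain at 0.5 SD is 2, 6 and 18 points: still positive, but smaller than with normal scores.
- The rank test and the score-scale interval can disagree under skew, in 16%, 15% and 10% of skewed runs at 0.5 SD.

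Multiplicity across the scores is a separate matter that adjustment does not address.

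**Conclusion.** The concern holds. The plan does not use first-assessment scores to adjust the one controlled comparison that bears on H1 to H3. That the adjustment is absent is plain from the text; only the size of the loss depends on assumptions.

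At 46/42 with normal scores, rank ANCOVA gains about 3 to 25 points of power at 0.5 SD, and 2 to 15 points at the 0.65 to 0.74 SD implied by the stated sample size. The gain is small at low correlation. Both tests hold about 5% type I error when patients are independent. Adjustment also protects against a chance imbalance in the measured score and removes part of a systematic one. How far the allocation rules raise the risk of imbalance cannot be computed, and no actual imbalance is shown. The change is a worthwhile, cheap improvement; the stated test is not invalid under true randomisation.

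**What to change.** - **Main test.** For each analysed score, regress the rank of the week 6 score on group and the rank of the first-assessment score of the same scale. State that this test decides.
- **Effect estimate.** Report the ANCOVA-adjusted mean difference on the score scale with an HC3 95% confidence interval. Do not use score-scale ANCOVA as the test: with strongly skewed scores at 0.5 SD its power is 67% (r = 0.3) and 74% (r = 0.5), against 78% for Mann-Whitney.
- **Sensitivity.** Keep the unadjusted Mann-Whitney. Where the rank test and the interval disagree, report both.
- **Limits to state.** Adjustment does not remove unmeasured allocation bias or same-room clustering. Residual bias depends on a baseline reliability that Cronbach's alpha does not fully measure.
- **Status.** Label the adjusted analysis as added after data collection.
- **Timing.** Data analysis places the third assessment at the sixth month, but Desing says "Than data collecting tools were re-administered to the both groups in the postpartum 6th week" and the procedure text under Secondary outcomes also gives the sixth week. These must be reconciled; the working above uses week 6.

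**Cost.** Revised Data analysis wording and two models per score. Ten scores (HPLP-II total, CES-D total, eight SF-36 subscales) need 2 × 10 = 20 fits; adding the six HPLP-II subscales makes 2 × 16 = 32. Check that the software provides HC3 errors. No new data or patients are needed.
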